6.1.3 Serious Adverse Events That Require Expedited Reporting

The NICHD will determine if individual serious adverse events a) meet the criteria for expedited reporting in accordance with 21CFR 312.32 IND safety reporting and b) if so, are promptly reported to the FDA and AN where indicated. See Section 6.4. Center PIs will determine if individual serious adverse events meet local IRB reporting criteria and report accordingly.

6.2 Characterizing Adverse Events

6.2.1 Severity/Intensity of Adverse Events

The Investigator will use the following general definitions to rate the severity/intensity of each adverse event. The NICHD Neonatal Toxicity Table is provided to guide the Investigators in judging severity/intensity in light of the NICU setting and the fragile condition of the extremely preterm infant (see MOP for the Neonatal Toxicity Table). The categories used in the CRF include: Mild, Moderate, Severe, Life Threatening and Death. Because of the nature of the study population, mild events will not be recorded as adverse events unless they are also unexpected.

Mild	The adverse event is transient, is very common in this population and easily tolerated by the subject.
Moderate	The adverse event causes the subject discomfort or interrupts the subject's usual function.
Severe	The adverse event causes considerable interference with the subject's usual function.
Life Threatening	The adverse event put the subject at substantial risk of dying at the time of the adverse event.
Death	Death was an outcome of the adverse event

6.2.2 Unexpected versus Expected Adverse Events

An unexpected adverse drug experience is defined as “[a]ny adverse drug experience, the specificity or severity of which is not consistent with the current Investigator’s Brochure; or, if an Investigator’s Brochure is not required or available, the specificity or severity of which is not

consistent with the risk information described in the general investigational plan or elsewhere in the current application,” as amended (21 CFR 312.32(a)).

The Investigator will code each adverse event as to whether this is an adverse event that is expected in this population, or if the event was unexpected in this population, or unexpected at the particular time in the course of the infant’s hospital course. The IB presents recent morbidity and mortality data on a large cohort of infants similar in GA to the infants who will enroll in the REDUCE-ROP (INS-3) study.

6.2.3 Relatedness of the Adverse Event to the Study Drug

The Investigator will use the following definitions to assess the relationship of the adverse event to the use of study drug: In addition, each adverse event will be coded as to whether it is related to study drug, or to a study procedure.

Definitely Related	An adverse event that is temporally and logically/medically directly related to administration of study drug or a study procedure.
Probably Related	An adverse event has a strong temporal relationship to study drug or recurs on re-challenge and another cause of event is unlikely or significantly less likely.
Possibly Related	An adverse event has a strong temporal relationship to the study drug and another cause of event is equally or less likely compared to the potential relationship to study drug.
Probably Not Related/Unlikely	An adverse event has little or no temporal relationship to the study drug and/or a more likely other cause of event exists.
Not Related/None	An adverse event is due to an underlying or concurrent illness or effect of another drug and is not related to the study drug (e.g., has no temporal relationship to study drug or has a much more likely other cause of event).

For causality assessments, events meeting the categories of definitely, probably, or possibly will be considered “associated.” Events that are probably not or not related will be considered “not associated.” In addition, when the Investigator has not reported a causality or deemed it not assessable, NICHD will consider the event associated.

6.2.4 Duration and Resolution of an Adverse Event

The adverse event recording form requires recording of the date of onset and resolution for each adverse event, (or documentation that it will not resolve) through 7 days after discontinuation of study drug. Serious adverse events and those events requiring IND safety reporting will be followed until resolution or determination that no resolution is possible.

6.3 Adverse Event Collection Period

All adverse events reported will be collected from the time of first study drug administration until 7 days following discontinuation of study drug. In addition, if an existing condition was present before study drug was started, but became substantially worse afterwards, it will also be reported as an adverse event. Serious adverse events and those events requiring IND safety reporting will be followed until resolution or determination that no resolution is possible.

6.4 Adverse Event Management and Reporting

All adverse events will be recorded on the study CRF and entered in the Data Management System (DMS). Timely mandatory reporting is required for adverse events that are:

1. Serious; and
2. Unexpected (unanticipated); and
3. Definitely, probably, or possibly related to the study drug.

Within 24 hours of discovering a serious adverse event (SAE), the study coordinator, in consultation with the Center's Investigator, will report these events to the NICHD, the Data Coordinating Center, and their own IRB per local requirements. A MEDWATCH form (FDA form 3500A) will be completed and submitted via FAX or e-mail within 24 hours of the Center being made aware of the SAE. Determination of whether the event may be unexpected and at least possibly related to study drug will be made by the clinical team in collaboration with the NICHD. If the serious adverse event meets criteria for expedited reporting, NICHD or their designee will notify the FDA and AN in accordance with set policy.

7 PROTOCOL DEVIATIONS

Compliance with the protocol will be monitored throughout the study. Any deviations or violations noted during conduct of the study are to be reported by the Center's Investigator or their designee. Due to the nature of the study, protocol deviations will need to be reported from both masked research personnel as well as unmasked pharmacy personnel separately. The MOP details the process for reporting protocol or pharmacy deviations or violations.

8 STATISTICAL METHODS AND DETERMINATION OF SAMPLE SIZE

8.1 Statistical and Analytical Plans

8.1.1 Independent Data Safety and Monitoring Committee

The NRN DSMC is composed of experienced experts in neonatology, biostatistics, bioethics, and developmental pediatrics. In addition, specific consultants relevant to the protocol also

participate in the DSMC, which for this study includes pediatric ophthalmologists. The current composition of the DSMC is listed in the MOP.

The NICHD NRN DSMC will be responsible for monitoring study safety and study performance as well as reviewing the results of the planned formal interim analyses.

The DSMC will monitor safety at a preplanned frequency when approximately 25%, 50% and 75% enrolled subjects have completed study therapy. At these intervals, the DSMC will review tabular summaries of adverse events and study data to determine whether there are any safety concerns that may impact continuation of the trial, or evidence that study procedures should be changed or the trial should be halted, only for reasons relating to the safety of the study subjects or inadequate trial performance (e.g., poor recruitment of subjects).

Specifically when monitoring safety, the DSMC will monitor the following at minimum:

- Recruitment by center and overall study progress.
- Randomization: to ensure that balance of baseline characteristics is being achieved by randomization.
- Rates of adverse events including serious adverse events, study drug-related adverse events, and deaths.
- Rates of clinical outcomes.
- Additionally, one formal interim analysis of efficacy and futility will be conducted after approximately 1000 infants have been enrolled and reached primary endpoint (Section 8.1.5).

8.1.2 Data Sets Analyzed

Depending on type, each analysis will be conducted within one or more of the following analysis populations. For the overall study analyses for publication, each population will include all infants that meet the population definition. For the regulatory submission analyses conducted within regulatory sub-studies, each sub-study will have a set of analysis populations per the definitions below that only comprise the infants assigned to that regulatory sub-study.

The safety population will include all infants who were randomized and received at least 1 dose of study drug. The safety population will be used for all safety analyses and infants will be grouped according to actual treatment received.

The ITT population is the primary population for formal efficacy analyses. This population includes all subjects randomized. For these analyses, subjects will be analyzed as part of the study arm to which they are assigned by randomization, regardless of the actual therapy they received.

8.1.3 Demographic and Other Baseline Characteristics

Demographic and baseline characteristics are recorded using the NRN GDB Protocol and include GA (weeks), GA stratum, birth weight, head circumference and length, age at start of study drug, sex, race, ethnicity, out born status, use of antenatal steroids, chorioamnionitis, delivery by cesarean section, 1 and 5 minute Apgar scores, use of chest compressions or resuscitation drugs in the delivery room, temperature at 1 hour of age and early onset sepsis (<72 hours). In addition, maternal data are collected on maternal pregnancy complications, type of insurance and educational level.

8.1.4 Efficacy Analyses

For scientific publication, Robust Poisson regression adjusting for center and GA strata will be used to estimate adjusted relative risk (and associated 95% CI) for myo-Inositol 5% Injection vs. placebo. The primary hypothesis will be tested based on a score test of the treatment effect in the Poisson regression model where the null hypothesis of no treatment effect on survival without severe ROP is rejected at either the interim or final analysis with a p-value consistent with an overall Type 1 error rate of 0.05 and a Bonferroni-type correction for multiple comparisons. (Casella and Berger 2002) For this analysis, individuals with indeterminate primary outcome status (i.e. alive through 55 weeks PMA and did not meet final acute ROP status but have ROP assessment data available), will go through an endpoint adjudication process and the resulting adjudicated endpoints will be used in the analyses. Individuals with completely missing outcomes (i.e. no ROP follow-up or death information available) or for which an adjudicated endpoint cannot be determined will be excluded from the analyses.

The following analyses will be conducted for a regulatory submission, provided there is evidence of efficacy. As suggested by the FDA, the primary outcome will be treated as a three level ordinal endpoint where the unfavorable outcomes are assigned a value of -1, indeterminate outcomes are assigned a value of 0, and favorable outcomes are assigned a value of +1. No adjudicated outcomes will be used.

The outcomes will be displayed in the following table:

Table 8. Outcomes Display of all enrolled subjects for the Regulatory Analysis

Outcome Status	Placebo (N1)	Inositol (N2)	Difference
Favorable (1)	n11 (n11/N1)	n21 (n21/N2)	XX
Unfavorable (-1)	n12 (n12/N1)	n22 (n22/N2)	XX
Indeterminate (0)	n13 (n13/N1)	n23 (n23/N2)	XX
Missing (by multiple imputation)	n14 (n14/N1)	n24 (n24/N2)	XX

This endpoint will be analyzed using a 2-sided Mantel-Haenszel chi-square test using modified ridit scores for ordinal data controlling for strata defined by study center and gestational age with

the analyses being completed separately within each of the two regulatory sub-studies. Individuals with completely missing outcomes (i.e. no ROP follow-up or death information available) will be imputed using a multivariate technique for multiple imputation. Formal inference based on the regulatory analyses is conditional on the findings of the primary analysis for scientific publication demonstrating a benefit (i.e. null hypothesis rejected at either the interim or final analysis with a p-value consistent with an overall Type 1 error rate of 0.05 and Bonferroni-type correction for multiple comparisons). This prioritization of analyses precludes the necessity of adjusting alpha for the additional regulatory analyses.

Various sensitivity analyses for both publication and regulatory submission will be performed to assess the impact of missing/indeterminate outcomes and robustness of the finding across multiple clinically relevant subpopulations. For example, if the results of the primary publication analysis of this multi-center trial are positive, then sensitivity analyses of the primary outcome will be performed to examine internal consistency of the study results. Specifically, consistency of treatment effect across subsets defined by GA strata and center separately will be assessed using the robust Poisson regression model. For GA strata, an interaction between GA strata and treatment will be added to the model. A p-value for the interaction >0.2 will be indicative of no interaction effect. If heterogeneity of treatment effect is present, then the likelihood ratio test (Gail and Simon 1985) will be used to determine whether the interactions are qualitative in nature (i.e., a test of the null hypothesis that inositol is at least as good as placebo in every subset of subjects vs. the alternative hypothesis that a cross-over effect exists such that placebo outperforms inositol in at least 1 of the subset of subjects). This same approach will also be used to assess consistency of treatment effect across centers. However, to ensure adequate power for identifying qualitative interactions among centers, the consistency analyses will be conducted with centers clustered into 4 subgroups defined by baseline prevalence of unfavorable ROP status (high vs. low) and expected enrollment size (large vs. small).

The decision to include adjudicated outcomes in the publication analyses as well as in sensitivity analyses for the regulatory submission is based on past studies showing that unfavorable ROP outcomes occur earlier in the hospital course and these subjects are normally under intense follow up efforts for the failure of their ROP to begin to regress (heal). Infants who meet favorable outcomes often have an indolent course of ROP, not meeting criteria for a favorable outcome until weeks after being discharged home. In the weeks following discharge, families often are under duress with the new baby at home and miss appointments or move away from study centers. As such, infants with incomplete follow up are almost always improving towards a favorable outcome.

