3 INTRODUCTION

3.1 Retinopathy of Prematurity

Retinopathy of prematurity (ROP) is a disorder of the developing retinal vasculature occurring in premature infants, that can progress to blindness. It occurs primarily in the lowest gestation infants and is a leading cause of blindness in the pediatric population both in developed, and increasingly in developing countries (Delpont 2002, Aggarwal 2002, Gilbert 2008, Quinn 2010). The incidence of any ROP is inversely proportional to gestation, occurring in over 95% of 23- to 24-week infants, but only 30% of 28-week survivors (Figure 1). In the most recent large study, from the Eunice Kennedy Shriver National Institute of Child Health and Human Development (NICHD) Neonatal Research Network (NRN), that determined the rate of severe ROP (receiving surgical peripheral retinal ablation to prevent possible retinal detachment), an average of 13% of the 24- to 27-week gestational age (GA) survivors developed severe ROP (SUPPORT 2010).

Figure 1: Rates of ROP in Survivors (NRN Unpublished Data: 2001 to 2003)

Interventions to prevent ROP have been a major research goal. Unfortunately the antioxidant vitamin E, d-penicillamine, and reduction in ambient light have not proven effective. Duration of oxygen exposure strongly correlates with ROP, and reasonable restriction of oxygen reduces severe ROP. However, if restriction is lowered to the bottom half of the accepted range, there is evidence of increased mortality (SUPPORT 2010). When severe ROP is detected by repeated indirect ophthalmology examinations, timely peripheral retinal ablation in severe cases can reduce progression to retinal detachment. However, even ROP that regresses (heals) spontaneously leads to increased rates of myopia, strabismus, amblyopia and acuity loss that is not correctable with lenses (Dobson 1994, CRYO-ROP 1996, CRYO-ROP 2001, Kushner 1982). Therefore, prevention of severe ROP, or even any ROP, must be the research goal for these infants.

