5.5.3 Method of Assigning Subjects to Treatment Groups

All infants will be centrally randomized using a secure, password protected web-based randomization system within the RAVE™ DMS available 24 hours/7 days per week via any computer with high-speed internet access. Directions for the randomization system are presented in the MOP. Eligible infants will be assigned a unique randomization number that allocates them in a 1:1 ratio to receive inositol or placebo. To ensure balance between the treatment groups, randomization will be stratified by center and by 2 gestational age risk strata (<26 and 26-27 weeks).

Randomization will be performed at the overall study level. For regulatory analyses, the randomized study population will be administratively split within study center in a pre-determined manner to define the regulatory sub-study A and sub-Study B (see SAP).

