8.2 Determination of Sample Size

Sample size calculations are based on the primary analysis of the single trial intended for scientific publication; however considerations for available statistical power are also presented for the submission analyses with the regulatory sub-studies.

The underlying prevalence of unfavorable ROP status (meeting criteria for Type I ROP or worse or expiring before ROP acute/final status is reached) is assumed to be 0.30 (SUPPORT 2010). For the scientific publication analyses based on a 2-sided Mantel-Haenszel test of the primary hypothesis with $\alpha=0.05$, a total sample size of 1672 infants (836 per group) provides a 90% power for detecting a treatment effect of ≥ 0.07 absolute reduction in unfavorable ROP status prevalence in the inositol arm compared to placebo.

It is also estimated that approximately 3-5% of the enrolled population may be lost to follow-up without sufficient information to obtain an adjudicated ROP endpoint. These subjects will be non-evaluable.

Accordingly, the final minimum required sample size to retain 90% power at an overall α level of 0.05 with one formal interim analysis for efficacy for detecting a ≥ 0.07 reduction in unfavorable ROP status prevalence is 1760 infants.

For the regulatory analyses, the study population will be administratively split in a pre-determined manner. To assess the power for the regulatory submission analyses within each sub-

study, simulations were conducted assuming that there will be 880 subjects within each sub-study, an underlying prevalence for sROP of 0.30, 5% subjects with completely missing outcome information and varying prevalence of indeterminate outcome and treatment effect (while the overall study is powered to test for minimally clinically significant treatment reduction, prior studies suggest a larger treatment effect may exist). If the true treatment effect is a 7% reduction in the myo-Inositol 5% Injection group, each sub-study analysis only has between a 56 to 62 percent chance of demonstrating a significant benefit for that sub-study. However, if the true treatment effect is an 8-9% reduction, the power for each sub-study analysis increases to between 69-83%.

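### The primary model adjusts for a two-level gestational-age stratum although gestational age in weeks is recorded; a prespecified week term would give a small gain in precision at no cost in data or alpha

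*Protocol*

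**What the plan says.** Protocol Section 8.1.4 names the model and its covariates for the primary publication analysis: "Robust Poisson regression adjusting for center and GA strata will be used to estimate adjusted relative risk". The hypothesis is tested with a score test from that model.

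The strata are the randomization factors. Section 5.5.3 states that "randomization will be stratified by center and by 2 gestational age risk strata (<26 and 26-27 weeks"). Section 5.2.1 sets no lower limit of gestation, so the younger level holds every enrolled infant below 26 weeks.

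A finer value is on file for each infant. The baseline variables in Section 8.1.3 "include GA (weeks), GA stratum, birth weight, head circumference and length". Section 5.2.1 adds that the assigned GA is the one used throughout the study.

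On prognosis, Section 3.1 describes any ROP as "occurring in over 95% of 23- to 24-week infants, but only 30% of 28-week survivors", and Section 5.6 gives the inverse relation to gestation as the reason for stratifying.

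Section 8.2 sizes the trial "based on a 2-sided Mantel-Haenszel test of the primary hypothesis", with a placebo rate of 0.30, an absolute reduction of 0.07 and 836 evaluable infants per group for 90% power. No credit is taken for covariate adjustment.

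**The concern.** If the risk of an unfavorable outcome changes from week to week inside a stratum, a two-level factor leaves part of the explainable variation in the error term. It also leaves the estimate exposed to chance differences between arms in GA week within a stratum. The younger stratum, open at its lower end, is where such differences could be largest. GA week is a baseline value already collected, so a model that uses it gains precision without extra infants or alpha. At stake is a slightly wider interval and slightly lower power for the one formally powered hypothesis, not its validity.

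**Working it through.** **1. The plan's own figure.** Inputs from Section 8.2: 0.30 versus 0.23, two-sided alpha 0.05, power 0.90. With mean rate 0.265:

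n per arm = [1.960 × √(2 × 0.265 × 0.735) + 1.2816 × √(0.30 × 0.70 + 0.23 × 0.77)]² / 0.07² = (1.2233 + 0.7974)² / 0.0049 = 833.3, so 834 per arm and 1668 in total.

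The plan states 836 and 1672. Power at 836 per arm is 0.901, and 1672 / 0.95 = 1760. The stated size therefore reproduces from an unadjusted two-proportion calculation.

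**2. Assumed weekly risks.** The protocol gives none for the primary composite. Three profiles were assumed for weeks 23/24/25/26/27, each scaled to a mean of 0.30, with a week mix of 8/17/23/26/26%:

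- mild: 0.49/0.41/0.33/0.25/0.19
- moderate: 0.63/0.48/0.34/0.21/0.14
- steep: 0.75/0.56/0.36/0.17/0.07

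**3. Share of outcome variance explained.** The total variance is 0.30 × 0.70 = 0.21. For the moderate profile, the stratum means are 0.438 (48% of infants) and 0.175 (52%). The stratum share is 0.48 × 0.52 × (0.438 − 0.175)² / 0.21 = 0.082. Summing over the five weeks in the same way gives 0.112.

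The variance ratio is (1 − R² for weeks) / (1 − R² for stratum). Power is Φ[(1.960 + 1.2816)/√ratio − 1.960], starting from exactly 90%. The N for 90% power is 1672 × ratio.

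| Profile | R² stratum | R² weeks | Ratio | Power | N for 90% |
|---|---|---|---|---|---|
| mild | 0.030 | 0.040 | 0.990 | 0.903 | 1655 |
| moderate | 0.082 | 0.112 | 0.967 | 0.909 | 1617 |
| steep | 0.164 | 0.219 | 0.935 | 0.918 | 1562 |

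With a younger or an older week mix, the reduction in variance stays between about 1% and 7%. In the three profiles shown, the stratum already captures 0.030/0.040 = 75%, 0.082/0.112 = 73% and 0.164/0.219 = 75% of what GA week explains.

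**4. Simulation of the named model.** Robust Poisson with a robust score test was run with N = 1672, 1500 replicates per profile, and randomization stratified by the two-level factor. Center was left out.

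- Mean model-based SE of the log relative risk, stratum to weeks: 0.0815 to 0.0812, 0.0797 to 0.0787, and 0.0768 to 0.0748. Squaring the ratios gives variance reductions of about 0.7%, 2.5% and 5.1%.
- Power: 0.903 to 0.903, 0.923 to 0.929, and 0.949 to 0.955. A separate simulation of the same kind gave gains of 0.5 to 1.5 points. The Monte Carlo SE of one power figure is about √(0.92 × 0.08/1500) = 0.7 points, although both models were fitted to the same simulated data.
- Type I error was 0.042 to 0.048 under either adjustment.

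**5. Chance imbalance within strata.** The extra variance explained by week in the moderate profile is (0.112 − 0.082) × 0.21 = 0.0063. The SD of the resulting error in the risk difference is √(4 × 0.0063/1672) = 0.0039, so about ±0.8 percentage points at 95%. The mild profile gives ±0.4 and the steep profile ±1.0, against a target effect of 7 points.

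**The case against.** The strongest reply is that nothing here is wrong. The model adjusts for exactly the factors used in randomization, which is valid and standard. Type I error is held, and the trial has its stated power with the model as written. All of that stands. A reader might infer that the primary analysis is biased or the trial underpowered; the documents support neither. Imbalance in GA week averages to zero over randomizations and is already reflected in the confidence interval. Adjustment removes most of it from the one trial actually run.

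A reader might also infer that the protocol shows the primary outcome falling steeply with each week. It does not. The rates in Section 3.1 are for any ROP, the lower one is at 28 weeks (outside the trial population), and death is not covered. The adjudicated rows of Table 6 for the multiple-dose Phase 2 study sum to 27/121 for all infants and 27/91 at 23-27 weeks. That implies 0/30 at 28-29 weeks, so the composite does vary with gestation, but again the contrast lies outside this trial's range.

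Two further replies carry some weight. The SAP may already plan a GA-week model as a sensitivity analysis; Section 8.1.4 nonetheless fixes the primary covariates. Categories with no lower limit could be sparse beside about 18 centers. That calls for a merging rule but is no obstacle: five weeks need three more parameters than two strata, with about 836 × 0.30 + 836 × 0.23 = 443 events expected under the design alternative.

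**Conclusion.** The point holds as a free but minor improvement. The primary model uses a two-level version of a baseline variable recorded in weeks and so gives up a little precision. For mild to steep assumed gradients, GA-week adjustment cuts the treatment-effect variance by about 1-6% and adds roughly 0-2 points of power, with the simulated gains toward the lower end. These figures depend on assumed weekly risks and an assumed week mix, and center was left out of the calculations. The direction does not depend on the exact profile, but the size does. Neither the validity of the primary test nor its stated 90% power turns on this change.

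**What to change.** In Section 8.1.4, before any unmasked data are seen, fix one covariate set for the primary robust Poisson model: center plus GA in completed weeks as categories. The interim analysis in Section 8.1.5 uses the same model, so the change should precede it.

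State a merging rule that ignores treatment arm: a youngest week with fewer infants than a prespecified count joins the next older week, and no category crosses the 26-week boundary. The randomization stratum then stays nested in the model.

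Keep the two-level stratum for randomization, for the GA interaction test and as a sensitivity model. Do not add optional birth weight or sex terms: their gain has not been quantified, and options would leave the primary model open.

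The cost is a wording change in the protocol and the matching SAP text. It needs no new data, no added infants and no alpha.
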